5 STATISTICAL CONSIDERATIONS

5.1 **Primary Endpoints**

- Current HIV seroconversion rates in high-risk men and women.
- Retention rates in high-risk men and women, as well as discordant couples.

5.2 Secondary Endpoints

• High-risk behaviors for HIV and STDs in newly enrolled participants.

A number of secondary risk factor endpoints will be assessed, including:

- ➢ Number of sex partners.
- > Presence and history of genital ulcer disease, urethritis and cervicitis.
- Presence of circumcision.
- ➢ Frequency of vaginal intercourse.
- ➢ Frequency of unprotected vaginal intercourse.
- ➢ Frequency of anal intercourse.
- ➢ Frequency of unprotected anal intercourse.
- Frequency of injection drug use.
- Frequency of sharing injection drug equipment
- > Frequency of sharing injection drug equipment without cleaning.
- ➢ Frequency of sexually transmitted diseases.
- > Frequency of serologic evidence of syphilis infection.
- Effective strategies to retain participants and overcome barriers to participation for upcoming HPTN clinical trials

As outlined below, we will calculate 6 and 12 month retention rates for the 400 newly identified and enrolled HIV uninfected women, as well as the 400 HIV discordant couples. We will also assess the factors identified at screening and follow-up that are associated with retention and/or loss to follow-up in these newly enrolled individuals. The in-depth interviews and focus groups will address a number of key questions a) what are the barriers to their participation in the studies; b) what do they think can be done to address their difficulties or obstacles to participation in the studies; c) What would motivate them to participate; d) what would motivate them to come back or continue with this study (this question is for those who have already enrolled and are coming for their follow up visits).

5.3 Sample Size Considerations

5.3.1 HIV Seroincidence

Our sample size is based on the number of new high-risk patients required to be enrolled over the next year to provide an estimate of HIV incidence. Separate HIV seroincidence rate will be computed for women and HIV-uninfected partners in our cohort study as the total number of HIV seroconversions divided by the total number of person-years of follow-up. Approximately 2000 new STD patients will be screened over the next year and 400 newly identified HIV-uninfected high-risk women and 400 HIV serodiscordant couples attending the STD clinics in Pune will be enrolled in order to estimate the current HIV incidence. Based on recent experience in our study, those participants screened 1999-2000 had a HIV prevalence rate of 19.0%. The overall HIV incidence in our cohort of initially HIV-uninfected individuals followed from May 1993 through April 2000 was

5.9/100 person years (Men=5.2/100PY, Women=9.8/100PY). Based upon the most recent experience of our study, the overall HIV incidence among those enrolled in the 1997-1999 cohort of HIV-uninfected individuals was 4.2/100 person years (Men=3.9/100PY, Women 5.6/100PY).

The null seroincidence used for sample size calculations will be the recent estimate of seroincidence in our cohort. This 034 protocol will enroll 400 women, as well as 400 HIV-uninfected partners of HIV-infected persons and follow them for 1 year, with an anticipated 90% semiannual retention.

The 400 high-risk women participants will accrue an estimated 348 person years of follow-up by July 2003. The study sample size will be adequate to estimate a 95% confidence interval for HIV incidence in the range of 3.37-8.74/100PY, assuming expected rates equal to those recently experienced in the cohort.

Amongst the discordant couples, the 400 HIV-uninfected partners will accrue 348 person years of follow-up, which will be sufficient to estimate a 95% confidence interval for seroincidence of 8.46-15.93/100PY, assuming an expected rate of 11.8/100PY (Quinn TC et al, NEJM 2000, 30;342(13):921-9. Note: there are no estimates of discordant couple transmission rates available for India).

The assumption used provides a conservative sample size estimate. While the target rate is 95% annual retention, the actual recent experience of the cohort is 81% semiannual retention. The assumption used in the sample size calculations of 90% semiannual retention will assure adequate power to measure a minimal level of incidence in the event that the target retention is not achieved.

[Note: Our site has successfully managed an average of 311 study visits per month over the past 8 years (median 305.5, range 150-475 visits per month), including screening, enrollment and follow-up visits. The present study will require 233 - 414 visits per month in the first year, and 54 - 234 visits per month in the second year. While the clinics will be operating at full capacity for the second half of year one, the workload will not overwhelm staff capabilities because half of the expected number of visits will consist of follow-up visits, which require considerably less staff time to complete than screening or enrollment visits]

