- Section 5.3.1 Approximately 2000 new STD patients will be screened over the next year and 400 540 newly identified high-risk women and 400 530 HIV serodiscordant couples attending the STD clinics in Pune will be enrolled in order to estimate the current HIV incidence.

This 034 protocol will enroll 400 540 women, as well as 400 530 HIV-uninfected partners of HIV infected persons and follow them for 1-year one and a half years with an anticipated 90% semiannual retention.

The 400 540 high-risk women participants will accrue an estimated 348 470 person years of follow-up by July 2003 August 2004.

Amongst the discordant couples, the 400 530 HIV-uninfected partners will accrue 348 461 person years of follow-up,

- Section 5.3.2 Amongst the 400 540 HIV-negative women enrolled in the study, we are targeting a 95% annual retention rate. Using that expected rate, the sample size of 400 540 will allow the estimation of the retention rate to within + 2.14% (95%CI). Similarly among the 400 530 HIV uninfected members of sero discordant couples we estimate that we will achieve 95% annual retention.
- Section 5.4 Overall retention rates will be calculated for all 1200 1600 subjects. In addition, the retention rates of the subset of 400 540 women and 400 530 discordant couples will be separately calculated.

Separate estimates of seroincidence will be calculated for the 400 540 women and the 400 530 HIV-uninfected partners.

To determine the current incidence of HIV among a cohort of 400 540 newly identified highrisk, HIV-negative women in Pune.

In addition, a separate estimate of the HIV incidence among 400 530 HIV-uninfected partners of HIV-infected subjects will also be estimated separately.

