5.4 Data Monitoring and Analysis

Close cooperation between the study site Investigator, Protocol Coordinator, Biostatistician, Data Managers, and other study team members will be necessary in order to track study progress, respond to queries about proper study implementation, and address other issues in a timely manner. Rates of accrual, follow-up, and protocol compliance will be monitored closely by the study team. Representatives of the HPTN CORE and SDMC also will evaluate these rates on a regular basis. If unexpected concerns arise, they will be addressed according to HPTN standard operating procedures.

The two primary objectives of this protocol will be:

- To determine the current incidence of HIV among a cohort of 400 newly identified high-risk, HIV-negative women in Pune. In addition, a separate estimate of the HIV incidence among 400 HIV-uninfected partners of HIV-infected subjects will also be estimated separately.
- To determine the retention rate in high-risk women, as well as HIV discordant couples.

Corresponding to each of the primary study objectives and outcomes, the following primary data analyses will be performed:

- An HIV seroincidence (and 95% confidence intervals) for the cohort study will be computed as the total number of HIV seroconversions divided by the total number of person-years of follow-up. Separate estimates of seroincidence will be calculated for the 400 women and the 400 HIV-uninfected partners.
- The number of enrolled participants retained for each study follow-up interval will be tabulated. Retention rates also will be calculated. The denominator for these calculations will be the total number of participants enrolled in the study. The numerator will include all participants who complete a Follow-up Pre-Test Visit during the interval and/or are known to have become HIV-infected or to have died during a previous interval. Overall retention rates will be calculated for all 1200 subjects. In addition, the retention rates of the subset of 400 women and 400 discordant couples will be separately calculated.
- Univariate and multivariate analysis will be performed for risk factors for incident HIV infection.

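### The Letter of Amendment raises person-years to 470 and 461 but leaves both incidence confidence intervals at the values for 348 person-years; the stated precision is wrong, in the conservative direction

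*Supplement*

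**What the plan says.** Version 1.0, section 5.3.1, sets precision separately for the two cohorts.

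- **Women.** "The 400 high-risk women participants will accrue an estimated 348 person years of follow-up by July 2003". From this the section derives its precision statement: "a 95% confidence interval for HIV incidence in the range of 3.37-8.74/100PY, assuming expected rates equal to those recently experienced in the cohort". The recent rate it reports for the 1997-1999 cohort "was 4.2/100 person years (Men=3.9/100PY, Women 5.6/100PY", so the expected rate for women is 5.6/100PY.
- **Partners.** 400 people accrue 348 person-years, and the precision is put in these words: "which will be sufficient to estimate a 95% confidence interval for seroincidence of 8.46-15.93/100PY". The rate behind that interval is given next, in the phrase "assuming an expected rate of 11.8/100PY".

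The Letter of Amendment of 24 May 2004 revises section 5.3.1. In the text as extracted, the struck-out and new figures stand next to each other:

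- Women: "high-risk women participants will accrue an estimated 348 470 person years of follow-up by July 2003 August 2004", that is, 348 becomes 470 with 540 enrolled.
- Partners: "HIV-uninfected partners will accrue 348 461 person years of follow-up", that is, 348 becomes 461 with 530 enrolled.

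The letter does not list the sentence with the women's interval. It reproduces the partners' sentence only up to the comma before its interval. It says that its changes will go into the next version of the protocol if there is one, and no later version is shown. The protocol as amended therefore still carries 3.37-8.74 and 8.46-15.93/100PY.

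**The concern.** An interval for a rate is fixed by the expected rate and the person-years. The letter changes the person-years by about 35% (470/348 = 1.35) and 32% (461/348 = 1.32), and leaves the rates alone, so the intervals must change. As it stands, the amended section says that 461 person-years give an interval computed from 348, and puts 470 person-years directly before another such interval.

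HIV incidence is the first primary objective, and section 5.3.1 says that the sample size rests on estimating it. These two intervals are the protocol's only statement of precision for incidence. An ethics committee or sponsor reading the letter to see what 140 more women and 130 more couples add to the incidence estimate would find no gain stated.

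**Working it through.** **Inputs.** Expected rates of 5.6/100PY (women) and 11.8/100PY (partners), section 5.3.1. Person-years of 348 for each cohort, section 5.3.1; 470 and 461, Letter of Amendment, section 5.3.1. Two-sided 95% level, section 5.4.

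**Formula.** The documents do not name a method. I used exact Poisson limits with expected count d = rate × PY:

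- lower = χ²(0.025; 2d) / 2 / PY
- upper = χ²(0.975; 2d + 2) / 2 / PY

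**Step 1. Reproduce the stated intervals at 348 person-years.**

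| Cohort | d | Exact Poisson, /100PY | Stated, /100PY |
|---|---|---|---|
| Women | 348 × 0.056 = 19.49 | 3.40-8.70 | 3.37-8.74 |
| Partners | 348 × 0.118 = 41.06 | 8.47-16.00 | 8.46-15.93 |

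All four limits agree within 1%. For women, cutting the count to 19 while holding the rate at 5.6/100PY gives 3.37-8.74, the stated figure to within rounding. A Wald interval (3.11-8.09; 8.19-15.41) does not fit. A log-normal one (3.59-8.73; 8.69-16.02) misses the lower limits. The stated intervals are therefore exact Poisson intervals for the old person-years.

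**Step 2. Same method at the amended person-years.**

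- Women: d = 470 × 0.056 = 26.32. Lower = 17.24/470 = 3.67/100PY; upper = 38.48/470 = 8.19/100PY.
- Partners: d = 461 × 0.118 = 54.40. Lower = 40.91/461 = 8.87/100PY; upper = 70.91/461 = 15.38/100PY.

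**Step 3. Size of the discrepancy.**

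| Cohort | Stated width | Width at amended PY | Stated/amended |
|---|---|---|---|
| Women | 8.74 - 3.37 = 5.37 | 8.19 - 3.67 = 4.52 | 1.19 |
| Partners | 15.93 - 8.46 = 7.47 | 15.38 - 8.87 = 6.51 | 1.15 |

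**Step 4. Sensitivity to rounding the count.** 26 events in 470 PY gives 3.61-8.11; 27 gives 3.79-8.36. 54 events in 461 PY gives 8.80-15.28; 55 gives 8.99-15.53. Each is clearly narrower than the stated interval. To one decimal, however, 26 and 54 events give 3.6-8.1 and 8.8-15.3, not 3.7-8.2 and 8.9-15.4, so the text must say whether the count was rounded.

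**Step 5. Are 470 and 461 themselves sound?** 348/400 = 0.870; 470/540 = 0.870; 461/530 = 0.870. The amended person-years are the old one-year yield per person multiplied by the new enrolment, while the letter extends follow-up to one and a half years. As an illustration, assume that everyone has 1.5 years available and that attrition is a constant hazard giving 90% retention per half-year: λ = -2 ln 0.9 = 0.211 per year, PY = n(1 - e^(-1.5λ))/λ. That gives about 694 (women) and 682 (partners). If seroconversion also ends follow-up, add 0.056 or 0.118 to λ; the results are about 668 and 628. At 668 and 628 the intervals would be 3.95-7.71 and 9.27-14.81/100PY, narrower again.

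**The case against.** **The error is harmless.** The old intervals are too wide, so nobody is promised precision that the study cannot deliver. The letter is dated May 2004, the women's person-years are projected to August 2004, and section 5.4 commits to reporting observed incidence with 95% intervals for each cohort. Observed intervals would soon replace the projection, and it is the measured incidence that the later trials need. This stands. It limits the consequence, but it does not make the amended sentences correct.

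**The gain is shown elsewhere.** The letter does state the increase in person-years itself, and section 5.3.2 restates retention precision for 540 women. The first is fair. The second does not help: it concerns retention, and it has the same omission. It keeps ±2.14%, where 1.96 × √(0.95 × 0.05/540) = ±1.84%.

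**Stronger readings that the documents do not support.** A reader might infer that the enlarged sample is inadequate; the direction of the error says the opposite. A reader might also infer that the women's interval never belonged to 348 person-years, because 19 events at 5.6/100PY implies 19/0.056 = 339. But 339 appears nowhere in the documents. The unrounded calculation at 348 is within 1% of the stated limits, and cutting 19.49 to 19 accounts for the rest. That is a rounding artefact.

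**The corrected limits rest on doubtful person-years.** This also stands. The August 2004 cut-off may explain a low figure for women, but no date is given for partners. If 470 and 461 are too low, the stale intervals are further out, so the doubt affects the replacement numbers and not the conclusion.

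**Conclusion.** The point holds. Section 5.3.1 as amended states 470 and 461 person-years together with intervals that come from 348, so the stated precision for the incidence objective is wrong. At the amended person-years the stated intervals are about 19% (women) and 15% (partners) too wide. The error is conservative and does not put the sample size in doubt. It should be corrected because it concerns the first primary objective and the correction is cheap.

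The percentages assume the plan's rates of 5.6 and 11.8/100PY, exact Poisson limits on the unrounded expected count, and 470 and 461 person-years taken at face value. The last is the weakest assumption.

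**What to change.** 1. Confirm 470 and 461 person-years against the stated one and a half years of follow-up, the 90% semiannual retention and the cut-off date, and give the cut-off date for partners as well as women.
2. If they are confirmed, replace 3.37-8.74 in amended section 5.3.1 with 3.7-8.2/100PY (26.3 expected events in 470 PY at 5.6/100PY), and 8.46-15.93 with 8.9-15.4/100PY (54.4 expected events in 461 PY at 11.8/100PY).
3. State that these are exact Poisson 95% limits on the unrounded expected count.
4. If the person-years change, recompute both intervals by the same formula.

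The cost is two intervals and one sentence on method in the letter, plus a check of the person-year projection. No change to design, enrolment or analysis is needed.

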5.3.2 Study Retention Rates

Amongst the 400 HIV-negative women enrolled in the study, we are targeting a 95% annual retention rate. Using that expected rate, the sample size of 400 will allow the estimation of the retention rate to within $\pm 2.14\%$ (95% CI). If the estimated retention were to drop to 90% the associated 95% CI is $\pm 3.0\%$, and if it were to drop as low as 80%, the sample size would allow the calculation of a 95% CI of $\pm 3.9\%$. Similarly, amongst the 400 HIV-uninfected members of serodiscordant couples we estimate that we will achieve 95% annual retention. This number of couples will allow for a 95% confidence interval of $\pm 2.14\%$, and for 90% retention the interval increases to $\pm 3.0\%$.

5.4 Data Monitoring and Analysis

Close cooperation between the study site Investigator, Protocol Coordinator, Biostatistician, Data Managers, and other study team members will be necessary in order to track study progress, respond to queries about proper study implementation, and address other issues in a timely manner. Rates of accrual, follow-up, and protocol compliance will be monitored closely by the study team. Representatives of the HPTN CORE and SDMC also will evaluate these rates on a regular basis. If unexpected concerns arise, they will be addressed according to HPTN standard operating procedures.

The two primary objectives of this protocol will be:

- To determine the current incidence of HIV among a cohort of 400 newly identified high-risk, HIV-negative women in Pune. In addition, a separate estimate of the HIV incidence among 400 HIV-uninfected partners of HIV-infected subjects will also be estimated separately.
- To determine the retention rate in high-risk women, as well as HIV discordant couples.

Corresponding to each of the primary study objectives and outcomes, the following primary data analyses will be performed:

- An HIV seroincidence (and 95% confidence intervals) for the cohort study will be computed as the total number of HIV seroconversions divided by the total number of person-years of follow-up. Separate estimates of seroincidence will be calculated for the 400 women and the 400 HIV-uninfected partners.
- The number of enrolled participants retained for each study follow-up interval will be tabulated. Retention rates also will be calculated. The denominator for these calculations will be the total number of participants enrolled in the study. The numerator will include all participants who complete a Follow-up Pre-Test Visit during the interval and/or are known to have become HIV-infected or to have died during a previous interval. Overall retention rates will be calculated for all 1200 subjects. In addition, the retention rates of the subset of 400 women and 400 discordant couples will be separately calculated.
- Univariate and multivariate analysis will be performed for risk factors for incident HIV infection.

Qualitative data analysis: In addition, corresponding to secondary study objectives, the HIV risk behaviors and assessment of barriers to enrollment and retention of study participants, in both the cohort and the community study will be described. In order to prepare for possible participation in the HPTN 052 trial, we will utilize qualitative and quantitative social science techniques to identify and address particular behavioral and social barriers to enrollment and retention of HIV discordant couples. In addition, the rate

of participant retention for each study follow-up interval, and across all four study visits, will be calculated. The baseline demographics and HIV risk behaviors of women and couples completing and not completing scheduled follow-up will be compared.

6 HUMAN SUBJECTS CONSIDERATIONS

6.1 Ethical Review

This protocol has been reviewed and approved by the local NARI Ethical Committee, the Central Ethical Committee of the Indian Council of Medical Research and the Johns Hopkins University JCCI (IRB). A Cooperative Project Assurance has been filed by the local NARI EC and has been approved by the OHRP of the USPHS. All attached consent forms have received preliminary review and approval by both the in-country IRB and the JHU JCCI. In order to prepare for the specific HPTN trials outlined in this study, we have submitted for review modifications to these previously approved consent forms addressing the issues of identifying and enrolling HIV discordant couples. The modified forms are attached in Appendix II and are under review by the local IRB and JHU JCCI. These modified consent forms will not be used until final approval is obtained from both of these ethical committees.

The local IRB/EC and the JHU JCCI will review this protocol at least annually. [name] will make safety and progress reports to the NARI IRB/EC at least annually, and within three months of study termination or completion. These reports will include the total number of participants enrolled in the study, the number of participants who completed the study, all changes in the research activity, and all unanticipated problems involving risks to human subjects or others.

6.2 Informed Consent

Written informed consent will be obtained from each study participant. The informed consent forms that we utilize (attached) have been developed for local use, translated/back-translated in 2 local languages (Hindi and Marathi) and describe the purpose of the study, the procedures to be followed, and the risks and benefits of participation, in accordance with all applicable regulations. Participants will be provided with a copy of their informed consent form if they are willing to receive them. Study staff will document the informed consent process as described in the study-specific procedures manual.

6.3 Confidentiality

All study-related information will be stored securely at the study site. All participant information will be stored in locked file cabinets in areas with limited access. All laboratory specimens, reports, study data collection, process, and administrative forms will be identified by a coded number only to maintain participant confidentiality. All records that contain names or other personal identifiers, such as locator forms and informed consent forms, will be stored separately from study records identified by code

number. All local databases will be secured with password-protected access systems. Forms, lists, logbooks, appointment books, and any other listings that link participant ID numbers to other identifying information will be stored in a separate, locked file in an area with limited access. Participants' study information will not be released without the written permission of the participant, except as necessary for monitoring by NIAID and/or its contractors (e.g., the DAIDS monitoring contractor), representatives of the HPTN CORE and/or SDMC, and/or the Indian Council of Medical Research (ICMR).

